## 7.6 CONSENT PROCEDURES AND DOCUMENTS

All patients or the appropriate power of attorney for health care will read and sign the informed consent document prior to enrollment. Members of the protocol team will

describe the protocol, alternative therapies, and the risks and benefits of each to the individual signing the consent.

#### 7.6.1 Telephone Consent

Telephone consent may be obtained via the following procedure: The informed consent document will be sent to the subject. An explanation of the study will be provided over the telephone after the subject has had the opportunity to read the consent form. The subject will sign and date the informed consent. A witness to the subject's signature will sign and date the consent.

The original informed consent document will be sent back to the consenting investigator who will sign and date the consent form with the date the consent was obtained via telephone.

A fully executed copy will be returned via mail for the subject's records.

The informed consent process will be documented on a progress note by the consenting investigator.

#### 7.6.2 Informed consent of non-English speaking subjects

If there is an unexpected enrollment of a research participant for whom there is no translated extant IRB approved consent document, the principal investigator and/or those authorized to obtain informed consent will use the Short Form Oral Consent Process as described in MAS Policy M77-2, OHSRP SOP 12 and 45 CFR 46.117 (b) (2). The summary that will be used is the English version of the extant IRB approved consent document. Signed copies of both the English version of the consent and the translated short form will be given to the subject or their legally authorized representative and the signed original will be filed in the medical record.

Unless the PI is fluent in the prospective subject's language, an interpreter will be present to facilitate the conversation (using either the long-translated form or the short form). Preferably someone who is independent of the subject (i.e., not a family member) will assist in presenting information and obtaining consent. Whenever possible, interpreters will be provided copies of the relevant consent documents well before the consent conversation with the subject (24 to 48 hours if possible).

We request prospective IRB approval of the use of the short form process for non-English speaking subjects and will notify the IRB at the time of continuing review of the frequency of the use of the Short Form.

## 8 SAFETY REPORTING REQUIREMENTS/DATA AND SAFETY MONITORING PLAN

Adverse events while on-treatment and for 30-days after the last dose of therapy will be reported to the NCI IRB according to the guidelines below. All serious adverse events occurring while on study will be reported as outlined in section 8.2.1. Since all therapy will be standard, commercially available therapy, data will not be reported to other organizations. The Principal Investigator will be responsible for data safety monitoring.

## 8.1 DEFINITIONS

### 8.1.1 Adverse Event

Any untoward medical occurrence in a human subject, including any abnormal sign (for example, abnormal physical exam or laboratory finding), symptom, or disease, temporally associated with the subject's participation in research, whether or not considered related to the subject's participation in the research.

### 8.1.2 Suspected adverse reaction

Suspected adverse reaction means any adverse event for which there is a reasonable possibility that the drug caused the adverse event. For the purposes of IND safety reporting, 'reasonable possibility' means there is evidence to suggest a causal relationship between the drug and the adverse event. A suspected adverse reaction implies a lesser degree of certainty about causality than adverse reaction, which means any adverse event caused by a drug.

### 8.1.3 Unexpected adverse reaction

An adverse event or suspected adverse reaction is considered "unexpected" if it is not listed in the investigator brochure or is not listed at the specificity or severity that has been observed; or, if an investigator brochure is not required or available, is not consistent with the risk information described in the general investigational plan or elsewhere in the current application. "Unexpected" also refers to adverse events or suspected adverse reactions that are mentioned in the investigator brochure as occurring with a class of drugs or as anticipated from the pharmacological properties of the drug, but are not specifically mentioned as occurring with the particular drug under investigation.

### 8.1.4 Serious

An Unanticipated Problem or Protocol Deviation is serious if it meets the definition of a Serious Adverse Event or if it compromises the safety, welfare or rights of subjects or others.

### 8.1.5 Serious Adverse Event

An adverse event or suspected adverse reaction is considered serious if in the view of the investigator or the sponsor, it results in any of the following:

- Death,
- A life-threatening adverse drug experience
- Inpatient hospitalization or prolongation of existing hospitalization
- Persistent or significant incapacity or substantial disruption of the ability to conduct normal life functions
- A congenital anomaly/birth defect.
- Important medical events that may not result in death, be life-threatening, or require hospitalization may be considered a serious adverse drug experience when, based upon appropriate medical judgment, they may jeopardize the patient

or subject and may require medical or surgical intervention to prevent one of the outcomes listed in this definition.

8.1.6 Disability

A substantial disruption of a person's ability to conduct normal life functions.

8.1.7 Life-threatening adverse drug experience

Any adverse event or suspected adverse reaction that places the patient or subject, in the view of the investigator or sponsor, at immediate risk of death from the reaction as it occurred, i.e., it does not include a reaction that had it occurred in a more severe form, might have caused death.

8.1.8 Protocol Deviation (NIH Definition)

Any change, divergence, or departure from the IRB-approved research protocol.

8.1.9 Non-compliance (NIH Definition)

The failure to comply with applicable NIH Human Research Protections Program (HRPP) policies, IRB requirements, or regulatory requirements for the protection of human research subjects.

8.1.10 Unanticipated Problem

Any incident, experience, or outcome that:

- Is unexpected in terms of nature, severity, or frequency in relation to
  - (a) the research risks that are described in the IRB-approved research protocol and informed consent document; Investigator's Brochure or other study documents, and
  - (b) the characteristics of the subject population being studied; **AND**
- Is related or possibly related to participation in the research; **AND**
- Suggests that research places subjects or others at a *greater risk of harm* (including physical, psychological, economic, or social harm) than was previously known or recognized.

## 8.2 NCI-IRB AND CLINICAL DIRECTOR REPORTING

### 8.2.1 NCI-IRB and NCI CD Expedited Reporting of Unanticipated Problems and Deaths

The Protocol PI will report in the NIH Problem Form to the NCI-IRB and NCI Clinical Director:

- All deaths, except deaths due to progressive disease
- All Protocol Deviations
- All Unanticipated Problems
- All non-compliance

As noted in section 8, this reporting applies to events while on-treatment and for 30-days after the last dose of therapy. Reports must be received within 7 days of PI awareness via iRIS.

### 8.2.2 NCI-IRB Requirements for PI Reporting at Continuing Review

The protocol PI will report to the NCI-IRB:

1. A summary of all protocol deviations in a tabular format to include the date the deviation occurred, a brief description of the deviation and any corrective action.
2. A summary of any instances of non-compliance
3. A tabular summary of the following adverse events:
  - All Grade 2 **unexpected** events that are possibly, probably or definitely related to the research;
  - All Grade 3 and 4 events that are possibly, probably or definitely related to the research;
  - All Grade 5 events regardless of attribution;
  - All Serious Events regardless of attribution.

**NOTE:** Grade 1 events are not required to be reported. Also, as noted in section 8, reporting is required only for events while on-treatment and for 30-days after the last dose of therapy.

## 9 PHARMACEUTICAL INFORMATION

### 9.1 RITUXIMAB

9.1.1 Source: rituximab will be purchased by the NIH Clinical Center Pharmacy Department from commercial sources.

9.1.2 Toxicity:

9.1.2.1 Hypersensitivity Reaction

9.1.2.2 Angioedema

9.1.2.3 Bronchospasm

9.1.2.4 Hypotension

9.1.2.5 Cardiac arrhythmia

9.1.2.6 Rash

9.1.2.7 Headache

9.1.2.8 Pruritus

9.1.2.9 Fatigue

9.1.2.10 Severe infusion reaction

9.1.2.11 Fatal reactions within 24 hours after administration

9.1.2.12 80% of fatal infusion reactions occurred in association with the first infusion

9.1.2.13 After an infusion reaction complex including 1 or more:

9.1.2.14 Hypoxia

- 9.1.2.15 Pulmonary infiltrates
- 9.1.2.16 Acute respiratory distress syndrome
- 9.1.2.17 Myocardial infarction
- 9.1.2.18 Ventricular fibrillation
- 9.1.2.19 Cardiogenic shock
- 9.1.2.20 Severe Mucocutaneous Reactions, some with fatal outcome
- 9.1.2.21 Constitutional symptoms
- 9.1.2.22 Fever
- 9.1.2.23 Chills
- 9.1.2.24 Infection
- 9.1.2.25 Asthenia
- 9.1.2.26 Headache
- 9.1.2.27 Abdominal Pain
- 9.1.2.28 Pain
- 9.1.2.29 Back Pain
- 9.1.2.30 Throat Irritation
- 9.1.2.31 Flushing
- 9.1.2.32 Cardiovascular System
- 9.1.2.33 Hypotension
- 9.1.2.34 Hypertension
- 9.1.2.35 Digestive System
- 9.1.2.36 Nausea
- 9.1.2.37 Diarrhea
- 9.1.2.38 Vomiting
- 9.1.2.39 Hematologic and Lymphatic System
- 9.1.2.40 Lymphopenia
- 9.1.2.41 Leukopenia
- 9.1.2.42 Neutropenia
- 9.1.2.43 Thrombocytopenia
- 9.1.2.44 Anemia
- 9.1.2.45 Metabolic and Nutritional Disorders
- 9.1.2.46 Angioedema
- 9.1.2.47 Hyperglycemia
- 9.1.2.48 Peripheral Edema
- 9.1.2.49 LDH Increase
- 9.1.2.50 Musculoskeletal System
- 9.1.2.51 Myalgia
- 9.1.2.52 Arthralgia

9.1.2.53 Nervous System

9.1.2.54 Dizziness

9.1.2.55 Anxiety

9.1.2.56 Respiratory System

9.1.2.57 Increased Cough

9.1.2.58 Rhinitis

9.1.2.59 Bronchospasm

9.1.2.60 Dyspnea

9.1.2.61 Sinusitis

9.1.2.62 Skin and Appendages

9.1.2.63 Night Sweats

9.1.2.64 Rash

9.1.2.65 Pruritus

9.1.2.66 Urticaria

### 9.1.3 Formulation and Preparation

#### 9.1.3.1 How Supplied

9.1.3.1.1 RITUXAN® (Rituximab) is supplied as 100 mg and 500 mg of sterile, preservative-free, single-use vials.

9.1.3.1.2 Single unit 100 mg carton: Contains one 10 mL vial of RITUXAN (10 mg/mL). (NDC 50242-051-21)

9.1.3.1.3 Single unit 500 mg carton: Contains one 50 mL vial of RITUXAN (10 mg/mL). (NDC 50242-053-06)

#### 9.1.3.2 Mixing and Dilution:

9.1.3.2.1 Use appropriate aseptic technique. Withdraw an amount of rituximab appropriate for a patient's dose and dilute it to a final concentration of 2 mg/mL in an infusion bag containing either 0.9% Sodium Chloride Injection, USP, or 5% Dextrose Injection, USP. Gently invert the bag to mix the solution. Discard any unused portion left in the vial. Parenteral drug products should be inspected visually for particulate matter and discoloration prior to administration.

### 9.1.4 Stability and Storage

9.1.4.1 Rituximab solutions for infusion may be stored at 2°—8°C (35.6°—46.4°F) for 24 hours. Rituximab solutions for infusion have been shown to be stable for an additional 24 hours at room temperature after storage for up to 24 hours under refrigeration. However, since rituximab solutions do not contain a preservative, diluted solutions should be stored refrigerated (2°—8°C). No incompatibilities between rituximab and polyvinylchloride or polyethylene bags have been observed.

9.1.4.2 Intact vials should be stored at 2°—8°C (36°—46°F). Do not use beyond the labeled expiration date. Rituximab vials should be stored in the original

packaging carton, protected from direct sunlight.

#### 9.1.5 Administration Procedures

9.1.5.1 DO NOT ADMINISTER AS AN INTRAVENOUS PUSH OR BOLUS.

9.1.5.2 Since transient hypotension may occur during rituximab infusion, consideration should be given to withholding antihypertensive medications 12 hours prior to rituximab infusion, and on the day of rituximab administration.

#### 9.1.5.3 First Infusion

9.1.5.3.1 The rituximab solution for infusion should be administered intravenously at an initial rate of 50 mg/h (25 mL/h). Rituximab should not be mixed or diluted with other drugs. If hypersensitivity or infusion reactions do not occur, escalate the infusion rate in 50 mg/h (25 mL/h) increments every 30 minutes, to a maximum of 400 mg/h (200 mL/h). If hypersensitivity (non-IgE-mediated) or an infusion reaction develops, the infusion should be temporarily slowed or interrupted. The infusion can continue at one-half the previous rate upon improvement of patient symptoms.”

#### 9.1.5.4 Subsequent Infusions

9.1.5.4.1 If the patient tolerated the first infusion well, subsequent rituximab infusions can be administered at an initial rate of 100 mg/h (50 mL/h), and increased by 100 mg/h (50 mL/h) increments at 30-minute intervals, to a maximum of 400 mg/h (200 mL/h) as tolerated. If the patient did not tolerate the first infusion well, follow the guidelines under First Infusion.

## 9.2 METHOTREXATE

9.2.1 Source: Preservative-free methotrexate will be purchased by the NIH Clinical Center Pharmacy Department from commercial sources.

9.2.2 Formulation: Methotrexate Injection, USP, is available in single-dose vials containing 50, 100, 200, 250, or 1000 mg of sterile, isotonic, preservative-free methotrexate sodium for parenteral administration.

9.2.3 Preparation: Dilute an amount of preservative-free methotrexate appropriate for a patient’s dose in (qs.) 1000 mL 5% Dextrose/0.45% Sodium Chloride Injection, USP, with an amount of sodium bicarbonate equivalent to what is given over 4 hours in hydration to maintain a patient’s urine pH within the range of 7-8.

9.2.4 Stability: When prepared as described above and stored at room temperature or under refrigeration, methotrexate is physically and chemically stable for at least 24 hours.

9.2.5 Storage: Store intact vials containing preservative-free methotrexate at controlled room temperature 15°–30°C (59°–86°F), and protect methotrexate-containing solutions from light. The extent of photodegradation correlates inversely with methotrexate concentration and is exacerbated by admixture with sodium bicarbonate.

9.2.6 Administration:

9.2.6.1 Pre-hydration: Patients will receive IV hydration with a suitable parenteral fluid containing sodium bicarbonate (e.g., 5% Dextrose with 0.45% Sodium Chloride Injection + 50-150 mEq sodium bicarbonate) to alkalinize the urine to a pH  $\geq 7$ , but  $\leq 8$ . Intravenous hydration should commence on Day 1 and continue at least until serum methotrexate levels are less than 0.5 mcmol/L. (See Sections [3.3.3.2.2](#), [3.3.3.3](#) and [3.4.3.4](#).)

9.2.6.2 Methotrexate  $6000 \text{ mg/m}^2$  will be administered by intravenous infusion over 4 hours after confirming that the recipient patient's urine pH is within the range  $\geq 7$  to  $\leq 8$ , and urine output is  $\geq 100 \text{ mL/hour}$ .

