  - 3.3.3.2 Urine alkalinization to pH  $\geq$ 7.0 to  $\leq$ 8.0 and urine output  $\geq$ 100 mL/hour often initially requires more NaHCO3 and more rapid hydration rates than will be required to maintain either or both parameters after they are achieved.
  - 3.3.3.2.1 The amount of sodium bicarbonate added to intravenously administered fluids should produce a solution with sodium content not greater than the concentration of sodium in 0.9% Sodium Chloride Injection ( $\leq$ 154 mEq/L).

3.3.3.2.2 Recommendations for initially achieving urine alkalinization to pH  $\geq 7.0$  to  $\leq 8.0$  and urine output  $\geq 100$  mL/hour:

Fluid	Administration Rate	Sodium Bicarbonate Content (per 1,000 mL)
0.45%NS	150 – 250 mL/h	50 – 75 mEq
0.2%NS		100 – 125 mEq
D5W/0.45%NS		50 – 75 mEq
D5W/0.2%NS		100 – 125 mEq
D5W		150 mEq

D5W: 5% Dextrose Injection, USP

NS: Sodium Chloride Injection, USP

3.3.3.3 In cases where the investigators feel that a patient can reliably maintain adequate hydration orally, intravenous hydration may be discontinued after the serum methotrexate level is  $<0.5$  mcMol/L.

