### Day 1 of each cycle:

1. Review all concomitant medications prior to day 1 of each cycle. Discontinue any drug that would have interaction with methotrexate excretion. See list below. No filgrastim within 24 hours before methotrexate administration.
2. Rituximab 375 mg/m^2
3. Start IV fluid hydration by 18:00, using one of the protocol specified alkalinized IVF order sets in CRIS for 06-C-0051
4. Order q6 hour urine pH  $\geq$  7.0 (00:00, 6:00, 12:00, 18:00) and **STRICT URINE OUTPUT** monitoring record urine output every hour
5. Draw the following blood work until methotrexate level is < or equal to 0.05 mcmol/L:
  - a. Hepatic panel every other day
  - b. CBC/Diff, Chem 7 daily

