**Day 2:**

1. 7 am: notify MD of urine pH and hourly UOP. If UOP < 100mL/hour or urine pH <7 or >8, adjust IVF.
2. Methotrexate 6000 mg/m^2. Order within the 06-C-0051 CRIS order set. Include Sodium Bicarbonate 45mEq as an additive. (May be adjusted between 25-75mEq depending on individual patient needs).
  - a. For creatinine clearance 60-100 mL, adjust methotrexate dose using formula: (Creatinine Clearance)/100 x 6000 mg/m^2
  - b. For creatinine clearance < 60ml/min, methotrexate **will NOT be administered**.
  - c. If episodic AST/ALT elevation > 10X upper limit normal on previous cycle, decrease methotrexate by 25%
3. Goal Start time: administer methotrexate starting between 9:00-10:00 am

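### The example pre-hydration fluid in Section 9.2.6.1 runs to twice the bicarbonate maximum given for the same fluid in Section 3.3.3.2.2 and, if read per 1,000 mL, exceeds the protocol's sodium limit at its upper end

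*Combined protocol and SAP*

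**What the plan says.** Section 3.3.3.2.1 limits the bicarbonate added to intravenous fluids: the amount "should produce a solution with sodium content not greater than the concentration of sodium in 0.9% Sodium Chloride Injection", which it puts at 154 mEq/L or less.

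The table in Section 3.3.3.2.2 follows, introduced as "Recommendations for initially achieving urine alkalinization to pH" 7.0 to 8.0. Its bicarbonate column is per 1,000 mL:

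- 0.45% saline, with or without 5% dextrose: 50-75 mEq
- 0.2% saline, with or without 5% dextrose: 100-125 mEq
- 5% dextrose alone: 150 mEq

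Section 9.2.6.1, on pre-hydration before methotrexate, gives as its example "5% Dextrose with 0.45% Sodium Chloride Injection + 50-150 mEq sodium bicarbonate". It states no volume. It refers the reader to Sections 3.3.3.2.2, 3.3.3.3 and 3.4.3.4, but not to Section 3.3.3.2.1, where the sodium limit is stated.

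Appendix 9 (Day 1, item 3) has hydration started "using one of the protocol specified alkalinized IVF order sets in CRIS".

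**The concern.** Sections 3.3.3.2.2 and 9.2.6.1 describe the same fluid for the same phase of treatment, bringing the urine to pH 7-8 before methotrexate, but give different bicarbonate ranges. The lower ends agree at 50 mEq. The upper ends are 75 and 150 mEq.

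The difference matters because each mEq of sodium bicarbonate brings one mEq of sodium, and half-strength saline already supplies half the permitted sodium. A pharmacist or nurse who prepares or checks a bag from the drug-information section could treat 150 mEq as allowed in a saline fluid, where the table would not allow it. The point is one of patient safety and internal consistency.

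**Working it through.** **Inputs**

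- Sodium limit: 154 mEq/L, the concentration in 0.9% saline (Section 3.3.3.2.1).
- Base sodium, in proportion to saline strength: 0.45% gives 154 x 0.45/0.9 = 77 mEq/L; 0.2% gives 154 x 0.2/0.9 = 34.2 mEq/L; 5% dextrose gives 0.
- Table range for the 0.45% fluids: 50-75 mEq per 1,000 mL (Section 3.3.3.2.2).
- Example range: 50-150 mEq, no volume (Section 9.2.6.1).
- Assumption 1: the example is per 1,000 mL, the unit of the table it cites.
- Assumption 2: bicarbonate stock of 1 mEq/mL, which the documents do not state.

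**Step 1. Comparison of ranges, with no sodium calculation.** 150/75 = 2.0. The example's upper end is twice the table's maximum for the same fluid.

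**Step 2. Volume convention.** Sodium can be computed in three ways for x mEq of bicarbonate and base sodium b:

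- On top of the litre: (b + x)/(1 + x/1000)
- Made up to one litre: b(1 - x/1000) + x
- Simple addition, ignoring volume: b + x

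The top of each table row should comply with the limit stated just above the table:

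| Fluid + bicarbonate | On top | Made up to 1 L | Simple |
|---|---|---|---|
| 0.45% saline + 75 | 141.4 | 146.2 | 152.0 |
| 0.2% saline + 125 | 141.5 | 154.9 | 159.2 |
| 5% dextrose + 150 | 130.4 | 150.0 | 150.0 |

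Only the on-top convention keeps every row within 154 mEq/L, so it is the consistent basis for judging Section 9.2.6.1 against the table.

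**Step 3. The example at 150 mEq per 1,000 mL, on top.** (77 + 150)/1.15 = 197.4 mEq/L. 197.4/154 = 1.282, so 28% over.

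**Step 4. Where the limit is reached, on top.** Solve (77 + x)/(1 + x/1000) = 154: x = 77/(1 - 0.154) = 91.0 mEq. The part of the stated range above the limit is (150 - 91)/(150 - 50) = 59%. At 50 mEq the sodium is 127/1.05 = 121.0 mEq/L and at 75 mEq it is 141.4 mEq/L, both within the limit.

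**Step 5. Sensitivity to the assumptions.**

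- Convention: at 150 mEq the other two give 77 x 0.85 + 150 = 215.4 and 77 + 150 = 227 mEq/L. The excess is present under all three; only its size changes.
- Stock strength, on top: 150 mEq would comply only if its own volume diluted the litre by 227/154 - 1 = 0.474 L, that is, a stock of 150/474 = 0.32 mEq/mL or weaker.
- Volume: if the example is not per 1,000 mL, 150 mEq meets the limit only in a larger base volume V. On top, 77V + 150 = 154(V + 0.15) gives V = 126.9/77 = 1.65 L. By simple addition, V = 150/77 = 1.95 L. Section 9.2.6.1 states neither.

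**The case against.** The strongest reply is that nobody need mix a bag from Section 9.2.6.1. The fluid is only an example, and the paragraph sends the reader to the table with the right amount for each fluid. The operative instructions are in Section 3.3.3, and Appendix 9 has hydration ordered from order sets. Urine pH outside 7-8 is notified (Section 3.3.3.1.2), electrolytes are checked daily (Section 3.8.3.6.4) and weights are taken daily (Appendix 9). All of this stands, and it makes the point minor. It does not remove the point: the example still contradicts the table it cites, and the paragraph does not refer to the sodium limit itself.

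It is also fair to say that the sodium excess is conditional. Without a volume, the text proves only a wider range with a missing denominator. Per 1,000 mL is the natural reading given the cross-reference, but it is an inference.

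A reader might take the excess to be 40% or 47% (215 or 227 mEq/L). Those figures use conventions under which the table's own 0.2% saline + 125 mEq row also exceeds the limit (about 155 or 159 mEq/L), so they are not a fair measure against that table.

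A reader might also infer that the methotrexate bag itself is overfilled, because Section 9.2.3 fills it "with an amount of sodium bicarbonate equivalent to what is given over 4 hours in hydration to maintain" urine pH and gives no number. The documents do not support that. Section 3.3.4.2.1 gives 25-75 mEq, and Appendix 9 gives 45 mEq with the note "May be adjusted between 25-75mEq depending on individual patient needs". Section 3.3.3.2 says that initial alkalinization often needs more bicarbonate and "more rapid hydration rates than will be required to maintain either or both parameters after they are achieved", so the table's initial rates cannot be carried over to the bag, and no maintenance rate is stated. The three texts are compatible.

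**Conclusion.** The point holds as a minor safety inconsistency. Without any assumption, Section 9.2.6.1 gives a range for 5% dextrose/0.45% saline that runs to twice the maximum in the table it cites, and omits the volume. On the per-1,000-mL reading, its upper end breaks the 154 mEq/L limit: about 197 mEq/L, 28% over, with bicarbonate added on top from an assumed 1 mEq/mL stock. The limit is reached at about 91 mEq.

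The range 50-150 mEq matches the lowest and highest entries of the whole table, so the all-fluid range may have been attached to one saline fluid. That is an inference about the cause, and the conclusion does not rest on it.

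A reader might infer that the protocol directs staff to give over-limit fluid, or that patients have received it. The documents do not support either: the example is optional, its lower part complies, and hydration is ordered from order sets whose contents are not shown. Sample size, power and the primary analysis are unaffected.

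**What to change.** In Section 9.2.6.1, change the example to 50-75 mEq sodium bicarbonate per 1,000 mL for 5% dextrose/0.45% saline, or delete the example and refer only to the table in Section 3.3.3.2.2. Section 9.2.3 needs no change, because 25-75 mEq for the methotrexate bag is already stated in Section 3.3.4.2.1 and Appendix 9.

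The cost is one wording change, with no effect on treatment schedules, order sets that already follow the table, or the analysis.
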